## **6. STATISTICAL ANALYSES**

Note that standard data derivation rule and stat methods are described in [Annex 1](#) and will not be repeated below. All Confidence Interval (CI) will be two-sided 95% CI.

### **6.1. Demography**

#### **6.1.1. Analysis of demographics/baseline characteristics planned in the protocol**

The following calculations will be performed for each group and for the pooled liquid vaccine group:

- The distribution of subjects enrolled among the study centres and countries will be tabulated as a whole and for each group.
- The numbers of subjects who withdraw from the study will be tabulated by group according to the reason for drop-out.
- The deviations from specifications for age and intervals between study visits will be tabulated by group.
- The median, mean, range and standard deviation of age (in weeks) at each HRV vaccine dose and of the gestational age will be computed by group. The median, mean and standard deviation of height (in centimetres) and weight (in kilograms) at

Visit 1 will be computed by group. The racial and sex composition will be presented. These calculations will also be performed by country.

- Summary of co-administered vaccinations (i.e., vaccinations given on the day of each HRV vaccine dose) and intercurrent vaccinations (i.e., vaccinations from birth up to Visit 3, excluding vaccination given on the day of HRV vaccine doses) will be summarized by group for the ES.

### **6.1.2. Additional considerations**

All demography summaries will be generated for the ES. The summary of age, height, weight, race and sex will also be provided for the PPS. Number and reason for elimination from PPS will be tabulated by group. Summary of important protocol deviations not leading to elimination will be provided by groups for the PPS.

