## **9. SUBJECT COMPLETION AND WITHDRAWAL**

### **9.1. Subject completion**

A subject who is available for the concluding contact foreseen in the protocol is considered to have completed the study.

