### **5.3. Important protocol deviation not leading to elimination from per-protocol analysis set**

The following important protocol deviations will be reported by groups:

- Forced randomization: In case of supplies shortage for the next assigned vaccine according to the randomization schedule at the clinical site, the randomization system will use the forced randomization procedure in order to continue to enrol and vaccinate subjects. The system moves seamlessly to the next treatment/randomization number for which vaccine supplies are available. The site will not be aware of the forced randomization event.
- Manual randomization: In case the randomization system is unavailable, the investigator has the option to perform randomization by selecting supplies available at the site according to a pre-defined rule. In case the randomization system is available, a vaccine different from the randomized treatment may have been administered at dose 1.
- Short follow-up: subjects with a safety follow-up period after the last dose of HRV vaccine that is less than 180 days.
- Vaccinated subjects without documentation of solicited symptoms i.e. for a vaccine dose administered, at least one solicited symptom is not documented as being present or absent.

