## **6.4. Analysis of safety**

### **6.4.1. Analysis of safety planned in the protocol**

The ES will be used for the analysis of safety.

The following calculations will be performed for each group and for the pooled liquid vaccine group:

The percentage of doses and of subjects reporting at least one symptom (solicited or unsolicited) during the 8 days (Day 0-Day 7) solicited follow-up period post vaccination will be computed, along with exact 95% CI. The same calculations will be done for symptoms (solicited or unsolicited) rated as grade 3 in intensity and for symptoms (solicited or unsolicited) assessed as causally related to vaccination.

The percentage of doses and of subjects reporting each individual solicited general symptom will be computed, over the 8 days (Day 0-Day 7) solicited follow-up period post vaccination, along with exact 95% CI. The same calculations will be done for each individual general solicited symptom rated as grade 3 in intensity, for each individual solicited general symptom assessed as causally related to vaccination and those that resulted in a medically attended visit.

The verbatim reports of unsolicited AEs will be reviewed by a physician and the signs and symptoms will be coded according to MedDRA. Every verbatim term will be matched with the appropriate Preferred Term. The percentage of subjects with unsolicited AEs occurring within 31 days (Day 0-Day 30) follow-up period after any dose with its exact 95% CI will be tabulated by group, and by preferred term. Similar tabulation will be done for unsolicited AEs rated as grade 3, for unsolicited AEs with causal relationship to vaccination and those that resulted in a medically attended visit.

The percentage of subjects reporting GE episodes from Dose 1 of HRV vaccine up to Visit 3 will be tabulated by group.

The percentage of subjects with presence of RV in GE stool samples collected from Dose 1 of HRV vaccine up to Visit 3 will be tabulated by group.

The percentage of GE episodes with no available stool results from Dose 1 of HRV vaccine up to Visit 3 will be tabulated.

The percentage of subjects who started taking at least one concomitant medication from HRV vaccination to Day 7 after vaccinations will be tabulated with exact 95% CI. The percentages of subjects who started taking at least one concomitant medication during the study period will be tabulated with exact 95% CI.

SAEs reported during the study period will be described in detail.

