**Template 2 Number of subjects enrolled by center - Exposed Set**

Country	Center	LIQ_A	LIQ_B	LIQ_C	LIQ_pool	LYO	Total	
		n	n	n	n	n	n	%
XXXX	PPD	38	38	38		37	151	12.6
	PPD	20	20	20		20	80	6.7
	PPD	30	30	29		29	118	9.8
	PPD	19	19	20		20	78	6.5
	All							
YYYYY	PPD	15	15	15		15	60	5.0
	PPD	22	22	23		22	89	7.4
	PPD	35	36	36		35	142	11.8
	PPD	28	28	28		28	112	9.3
	PPD	20	21	20		21	82	6.8
	PPD	22	23	22		23	90	7.5
	PPD	22	23	22		23	90	7.5
	PPD	27	27	27		27	108	9.0
	All							
All	All	298	302	300		300	1200	100

<group description >

n = number of subjects included in each group or in total for a given center or for all centers

All = sum of all subjects in each group or in total (sum of all groups)

% = n/All x 100

**Template 3 Number of subjects vaccinated, completed and withdrawn with reason for withdrawal entire study period- Exposed Set**

	LIQ_A	LIQ_B	LIQ_C	LYO	Total
Number of subjects vaccinated	298	302	300	300	1200
Number of subjects completed	297	301	298	297	1193
Number of subjects withdrawn	1	1	2	3	7
Reasons for withdrawal :					
Serious Adverse Event	0	0	0	1	1
Non-serious adverse event	0	0	0	0	0
Protocol violation	0	0	0	0	0
Consent withdrawal (not due to an adverse event)	1	0	1	2	4
Migrated/moved from study area	0	1	1	0	2
Lost to follow-up (subjects with incomplete vaccination course)	0	0	0	0	0
Lost to follow-up (subjects with complete vaccination course)	0	0	0	0	0
Others	0	0	0	0	0

LIQ\_A = HRV vaccine liquid formulation Lot A

LIQ\_B = HRV vaccine liquid formulation Lot B

LIQ\_C = HRV vaccine liquid formulation Lot C

LYO = HRV vaccine lyophilised formulation

Vaccinated = number of subjects who were vaccinated in the study

Completed = number of subjects who completed study visit 3

Withdrawn = number of subjects who did not come for study visit 3

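### SAP 6.1.2 summarises short follow-up on the immunogenicity per-protocol set instead of the Exposed Set, and Template 3 defines completion by Visit 3, contrary to Protocol 9.1 and 9.2.1

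*SAP*

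**What the plan says.** All SAP references are to Amendment 1.

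- **Deviations.** SAP 5.3 names four important deviations that leave an infant in the PPS. Two concern randomisation (forced and manual). The other two concern safety data: short follow-up, defined as "subjects with a safety follow-up period after the last dose of HRV vaccine that is less than 180 days", and "Vaccinated subjects without documentation of solicited symptoms".
- **Set for their summary.** SAP 6.1.2: "Summary of important protocol deviations not leading to elimination will be provided by groups for the PPS". The same section says of the other tables: "All demography summaries will be generated for the ES".
- **Set for safety.** SAP 6.4.1: "The ES will be used for the analysis of safety".
- **Who is outside the PPS.** SAP 5.2.2, code 2100, removes anyone without a post-vaccination anti-rotavirus IgA result.
- **Completion.** Protocol 9.1: "A subject who is available for the concluding contact foreseen in the protocol is considered to have completed the study". Protocol 9.2.1 defines withdrawal as the converse, by the same contact. The footnote to Template 3 in SAP Annex 3 reads: "Completed = number of subjects who completed study visit 3". Its next line defines withdrawn as not attending Visit 3. The title of that template nevertheless covers the whole study period.

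**The concern.** The count of infants with short follow-up helps a reader judge how complete the six-month safety surveillance was. It therefore belongs on the set in which safety is reported. On the PPS it omits, by construction, any infant who left before Visit 3, because that infant has no Visit 3 serology. Those infants have the shortest follow-up of all.

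The completeness of follow-up matters here for three reasons:

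- Serious adverse events from Dose 1 to study end are a secondary endpoint.
- SAP 11.1.5 treats a vaccinated infant with no report as having no event.
- Protocol 1.3.1 lists the six-month follow-up among the mitigations for risks that include intussusception.

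If Template 3 were also run as footnoted, an infant lost between Visit 3 and Month 7-8 would be shown as having completed the study.

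**Working it through.** **1. The plan's own figure.** Protocol 10.3 targets 1280 evaluable infants and assumes that about 20% of those enrolled are not evaluable: 1280 / (1 - 0.20) = 1600, or 400 per group. This reproduces the stated enrolment.

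**2. Size of the omitted part.** 1600 - 1280 = 320 infants, which is 320 / 1600 = 20%, or about 80 per group. The mock data, copied from an earlier study, give a similar share. Template 5 shows 998 of 1200 in the PPS (83.2%), so 1200 - 998 = 202 (16.8%) are outside it.

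**3. Losses before Visit 3.** None of these infants can be in the PPS (code 2100), so none can enter the short follow-up count. They do appear in Template 3 as withdrawn, even on its literal footnote. The documents give no expected rate. The mock Template 3 shows 7 of 1200 (0.6%), which scales to 1600 x 7 / 1200 = about 9 infants.

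**4. Losses after Visit 3.** The documents give no rate, so this step is an assumption shown as a range. Taking those 9 out of both numbers, the share outside the PPS among infants still in the study is (320 - 9) / (1600 - 9) = 311 / 1591 = 19.5%. If later loss is unrelated to PPS membership:

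| Assumed loss after Visit 3 | Infants lost (of 1600) | Completed under the literal Template 3 | Also outside the PPS count (x 0.195) |
|---|---|---|---|
| 2% | 32 | 32 | about 6 |
| 5% | 80 | 80 | about 16 |
| 10% | 160 | 160 | about 31 |

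If every later loss fell among infants outside the PPS, the last column would equal the second. That is the extreme case.

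**5. Whether other ES tables fill the gap.**

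- *Withdrawals.* SAP 6.1.1, read with 6.1.2, requires withdrawals by group and reason on the ES. With the Protocol 9.2.1 definition this would capture losses up to the concluding contact. With the Template 3 footnotes it would not.
- *Intervals.* SAP 6.1.1 also requires interval deviations on the ES, and Protocol Table 5 includes the safety contact at 180-210 days. Template 7 as drawn stops at the post-Dose 2 sample. Its N is infants with available results, so an infant with no contact would drop out of the denominator.
- *Early contacts.* An infant whose concluding contact comes before day 180 is complete under Protocol 9.1 but has short follow-up under SAP 5.3. A withdrawal table cannot show this infant, so the short follow-up count is needed on the ES in its own right.
- *Undocumented symptoms.* Template 17 gives symptom-sheet return on the ES. SAP 6.4.2 adds a documented-dose analysis if more than 5% of doses are undocumented. Sheet return is coarser than the SAP 5.3 criterion of at least one symptom not documented.

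**The case against.** The strongest reply is that the second half rests on a mock footnote. SAP Annex 3 says that displays, titles and footnotes are illustrative and will be adapted, and the templates still carry the earlier study's dates and limits. On this view the SAP text governs: withdrawals are tabulated on the ES, and the protocol defines withdrawal by the concluding contact. Template 4 (visit attendance and a list of withdrawn infants) is also on the ES, though its body is not in the reviewed text. Template 35 has a completed row on the ES with no Visit 3 restriction.

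Much of this stands. It rules out a stronger reading that a reader might infer: that both safety deviations are visible only in the PPS and that losses from the six-month follow-up go largely uncounted. The documents do not support it. Undocumented symptoms have ES tables of their own, leavers before Visit 3 appear in Template 3, and the governing text calls for withdrawals on the ES. Nor can it be said that any infant appears nowhere, since Template 4 cannot be inspected.

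Two things remain. The disclaimer on templates does not reach SAP 6.1.2, which is governing text. Annex 3 also allows only editorial or minor changes without an amendment and refers the adaptation to a list of outputs that is not in the reviewed documents. SAP 8.2 cites the same version of that list for the Visit 3 analysis (E1_05) and the final analysis (E1_01), so nothing visible switches the definition of completion between them.

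**Conclusion.** The point holds in limited form. The SAP 6.1.2 rule would give a short follow-up count that omits a planned 320 of 1600 infants (20%) and, by construction, all those lost before Visit 3. It therefore does not describe the population in which safety is reported. Template 3, read literally, contradicts both its own title and Protocol 9.1 and 9.2.1.

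The 320 rests on the protocol's 20% assumption, which refers to enrolled infants; I take nearly all of them to be vaccinated. The number of affected infants rests on loss rates that the documents do not give. If 2-5% are lost after Visit 3, unrelated to PPS membership, 32 to 80 would be labelled completed, and about 6 to 16 of those would also be outside the deviation summary.

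A reader might go further and infer that the serious adverse event percentages are biased. The documents do not show that: they give no follow-up rates, and the safety analyses are descriptive. The co-primary analyses, the sample size and the safety analysis set are unaffected. This is a matter of complete and consistent safety reporting, and it should be corrected.

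**What to change.** 1. In SAP 6.1.2, provide the summary of non-eliminating deviations for the Exposed Set. A PPS version may be kept as well; it is most useful for the two randomisation deviations.
2. For the final analysis (E1_01), define completed and withdrawn in the Template 3 footnotes by the concluding contact, as Protocol 9.1 and 9.2.1 do. Keep the Visit 3 definition for E1_05 and say so in the table title.
3. Optionally, add the 180-210 day contact to Template 7 and show separately the infants with no contact.

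The two main changes cost one sentence and one footnote, with the same program run on another set. No data collection, design feature or confirmatory analysis changes.

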## **6.2. Exposure**

### **6.2.1. Analysis of exposure planned in the protocol**

Not applicable

### **6.2.2. Additional considerations**

The number of doses administered will be tabulated for each group.

## **6.3. Immunogenicity**

### **6.3.1. Analysis of immunogenicity planned in the protocol**

The primary analysis will be based on the PPS for analysis of immunogenicity. If, in any vaccine group, the percentage of vaccinated subjects with serological results excluded from the PPS for analysis of immunogenicity is 5% or more, a second analysis based on the ES will be performed to complement the PPS analysis.

#### **6.3.1.1. Within groups assessment**

The following calculations will be performed for each group and for the pooled liquid vaccine group.

- For each group, at each time point that anti-rotavirus IgA is measured,
  - Seropositivity/seroconversion rates and their exact 95% CI will be computed,
  - Percentage of subjects with anti-RV IgA antibody concentrations  $\geq 90$  U/mL and their exact 95% CI will be computed.
  - GMCs and their 95% CIs will be computed.
- The above mentioned descriptive analyses will also be performed by country.

- The distribution of anti-RV IgA antibody concentrations at Visit 3 will be displayed using Reverse Cumulative Curves (RCCs).

#### **6.3.1.2. Between groups assessment**

- The 95% CI for the ratio of anti-RV IgA antibody GMCs at Visit 3 between any pair of the three lots of the HRV liquid vaccine will be computed (first co-primary objective).
- The asymptotic standardized 95% CI for the difference in seroconversion rate at Visit 3 between the PCV-free liquid HRV vaccine (pooled HRV liquid groups) and lyophilised HRV vaccine will be computed (second co-primary objective).
- The 95% CI for the ratio of anti-RV IgA antibody GMCs at Visit 3 between the PCV-free liquid HRV vaccine (pooled HRV liquid groups) and lyophilised HRV vaccine will be computed (third co-primary objective).

#### **6.3.1.3. Statistical Methods**

- The exact CIs for a proportion within a group will be calculated using SAS [see section 11.1].
- The standardized asymptotic CI for the group difference in proportion will be calculated using SAS [see section 11.1].
- The CI for GMCs will be obtained within each group separately. The CI for the mean of log-transformed concentration will be first obtained assuming that log-transformed values were normally distributed with unknown variance. The CI for the GMCs will then be obtained by exponential-transformation of the CI for the mean of log-transformed concentration.
- The GMC group ratio will be obtained using an ANOVA model on the logarithm-transformed concentrations. The ANOVA model will include the vaccine group and the country as fixed effects. The GMC ratio and their 95% CI will be derived by exponential-transformation of the corresponding group contrast in the model.

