### **5.2.2. Randomisation of treatment**

#### **5.2.2.1. Randomisation of supplies**

The numbering of supplies will be performed at GSK Biologicals, using a block scheme randomisation in MATerial EXcellence (MATEX), a program developed for use in Statistical Analysis System (SAS®) (Cary, NC, USA) by GSK Biologicals. Entire blocks will be shipped to the study centres/warehouse(s).

To allow GSK Biologicals to take advantage of greater rates of recruitment than anticipated at individual centres in this multi-centre study and to thus reduce the overall study recruitment period, an over-randomisation of supplies will be prepared.

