##### **5.2.2.2.1. Study group and treatment number allocation**

The target will be to enrol 1600 eligible subjects who will be randomly assigned to four study groups in a 1: 1: 1: 1 ratio (approximately 400 subjects in each group).

Allocation of the subject to a study group at the investigator site will be performed using SBIR. The randomisation algorithm will use a minimisation procedure accounting for

centre and country. Minimisation factors will have equal weight in the minimisation algorithm.

After obtaining the signed and dated ICF from the subject's parent(s)/LAR(s) and having checked the eligibility of the subject, the site staff in charge of the vaccine administration will access SBIR. Upon providing the subject identification number, the randomisation system will determine the study group and will provide the treatment number to be used for the first dose.

The number of each administered treatment must be recorded in the eCRF on the Vaccine Administration screen.

When SBIR is not available, please refer to the SBIR user guide or the Study Procedures Manual (SPM) for specific instructions.

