#### 6.4. Replacement of unusable vaccine doses

In addition to the vaccine doses provided for the planned number of subjects (including over-randomisation when applicable), at least 30% additional vaccine doses will be supplied to replace those that are unusable.

The investigator will use SBIR to obtain the replacement treatment number. The replacement numbers will be allocated by dose. The system will ensure, in a blinded manner, that the replacement applicator matches the formulation the subject was assigned to by randomisation.

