## 11. ANNEX 1 STANDARD DATA DERIVATION RULE AND STATISTICAL METHODS

### 11.1. Statistical Method References

The exact two-sided 95% CIs for a proportion within a group will be the Clopper-Pearson exact CI Clopper CJ, Pearson ES. The use of confidence or fiducial limits illustrated in the case of binomial. *Biometrika*. 1934;26:404-413.

The standardised asymptotic two-sided 95% CI for the group difference in proportions is based on the method described in the following paper: Robert G. Newcombe, interval estimation for the difference between independent proportions: comparison of eleven methods, *Statist Med*. 1998; 17, 873-890. The standardised asymptotic method used is the method six.

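### Does the seroconversion comparison need a country-adjusted interval because country is a minimisation factor and the GMC analyses adjust for it?

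*SAP*

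**What the plan says.** Protocol Section 5.2.2.2.1: "The randomisation algorithm will use a minimisation procedure accounting for" centre and country, and "Minimisation factors will have equal weight in the minimisation algorithm".

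SAP Section 6.3.1.3 treats the two kinds of endpoint differently. For GMC ratios, "The ANOVA model will include the vaccine group and the country as fixed effects". For seroconversion, "The standardized asymptotic CI for the group difference in proportion will be calculated using SAS", and Section 11.1 adds "The standardised asymptotic method used is the method six". That is a plain two-sample score interval. Protocol Sections 2.1 and 10.9.1 give the same criterion (lower limit at or above -10%, pooled liquid minus lyophilised) and the same method.

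Other planned outputs bear on country:
- enrolment by centre, country and group (SAP 6.1.1);
- deviations such as forced and manual randomisation, by group in the per-protocol set (SAP 5.3 and 6.1.2);
- seroconversion rates with exact intervals, by group and for pooled liquid, repeated by country in the per-protocol set (SAP 6.3.1.1 and 6.3.2);
- a second analysis on the Exposed Set if, in any group, at least 5% of vaccinated subjects with serology are excluded (SAP 6.3.1).

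**The concern.** An analysis normally respects the factors used in allocation, and this plan does so for two of its three co-primaries. The third comes from the same assay, visit and analysis set, and its comparison ignores country.

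A route to harm can also be described. The per-protocol set is not the allocated set, since about 20% of subjects are expected to be non-evaluable (protocol Section 10.3). Subjects affected by forced randomisation stay in it, and under that procedure "The system moves seamlessly to the next treatment/randomization number for which vaccine supplies are available". Shortages arise at sites, so they could cluster by country. If seroconversion differs between countries and the arms end up with different country mixes, the unadjusted difference shifts with the mix. At stake would be a non-inferiority conclusion that partly reflects where infants were enrolled, with no pre-specified adjusted estimate to test it.

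**Working it through.** **Inputs.** Evaluable subjects 960 and 320, margin -10 points, one-sided 2.5% (protocol 10.3.1 and 10.3.3). The documents give no seroconversion rates by country. I assume rates from the studies in Table 16, whose extremes are 76.8% and 93.9%. The only country share given is about 25% for the US (protocol 4.1).

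**Method.** Unadjusted: z = (p_L - p_C + 0.10) / sqrt(v), where v is the variance at the maximum-likelihood rates restricted to a difference of -10 points. Stratified: z = sum w_k(p_Lk - p_Ck + 0.10) / sqrt(sum w_k^2 v_k), with w_k = n_Lk n_Ck/(n_Lk + n_Ck). Non-inferiority is met when z is at least 1.96.

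**Reproducing the plan's figures.** The unadjusted method applied to the counts in mock Template 10 (661/746 and 228/252) gives -5.83 to 2.85, the Template 13 limits with the sign reversed. Summing over both binomials gives these powers against Table 18:

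| Rate in both arms | Computed | Table 18 |
|---|---|---|
| 75% | 96.2% | 96.0% |
| 80% | 98.4% | 98.1% |
| 85% | 99.7% | 99.5% |
| 90% | 99.99% | 99.9% |

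**Precision with balanced countries.** Take two equal countries at 76.8% and 93.9%, mean 85.35%.
- Total variance per subject: 0.8535 x 0.1465 = 0.1250.
- Within-country variance: (0.768 x 0.232 + 0.939 x 0.061)/2 = 0.1177.
- Ratio 0.942, square root 0.970. The unadjusted half-width of 4.49 points would fall by 4.49 x 0.03 = 0.13 points, or by 0.11 from the score limits themselves, against a 10-point margin.
- With the eight Table 16 rates equally weighted, it falls from 4.28 to 4.25.

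**Error and power** (400,000 simulated trials per scenario, 200,000 for random exclusions; Monte Carlo standard error about 0.02 to 0.04 points on the error rates). Error is at a true -10 points in every country.

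| Scenario | Unadjusted | Stratified |
|---|---|---|
| Balanced, 76.8/93.9%: error | 2.34% | 2.63% |
| Balanced, 76.8/93.9%: power at equal rates | 99.78% | 99.77% |
| Balanced, eight Table 16 rates: error | 2.56% | 2.68% |
| Random 20% exclusions, 76.8/93.9%: error | 2.42% | 2.66% |
| Lyophilised arm +3 points in low-rate country, 76.8/93.9%: error | about 4.0% | 2.6-2.7% |
| Same, -3 points: error | 1.3% | 2.6-2.7% |
| 25/75 split at 76.8/88.6%, +3 points: error | 3.7% | 2.7% |
| Same split, -3 points: error | 1.7% | 2.6% |

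With balance at 76.8/93.9%, the two methods reach different conclusions in 0.29% of trials at the margin and 0.02% at equal rates. Averaging the two directions of imbalance gives (4.0 + 1.3)/2 = 2.65%, the stratified value. For a 25/75 split at milder rates of 86.0% and 88.6%, also from Table 16, the +3-point case gives 2.9% unadjusted.

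**Mix needed to overturn the expected result.** With equal observed rates near 85%, the score lower limit is about -4.2 points. A 3-point mix difference at a 17.1-point rate gap moves the estimate by 0.03 x 17.1 = 0.5 points. If the limit moves one-for-one with the estimate, reaching -10 needs a difference in country share of (10 - 4.2)/17.1 = 34 points, or (10 - 4.2)/11.8 = 49 points at 76.8% against 88.6%.

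**Is drift likely?** Minimisation on centre and country works against it. Supplies leave in whole randomisation blocks, "an over-randomisation of supplies will be prepared" (protocol 5.2.2.1), and "at least 30% additional vaccine doses will be supplied to replace those that are unusable" (protocol 6.4). A lasting shortage of one arm's vaccine, confined to countries with unusual seroconversion rates, is hard to construct from this. Random loss from the per-protocol set does not inflate the error, as the table shows.

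**The case for a change.** The best argument for acting is that a stratified interval costs a sentence or two and one table row, and would hold the error at 2.6-2.7% whatever the country mix. Descriptive tables can show drift but do not state whether the -10% conclusion survives it, and an adjustment chosen after unblinding can be challenged. The sponsor already treats country as relevant to this antibody response.

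Part of this stands. No country-adjusted seroconversion difference is planned, and under a systematic imbalance in the unfavourable direction the unadjusted error would exceed 2.5%. Centre, the other minimisation factor, is in none of the three comparisons.

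The rest does not make it a fault. A country term for log concentrations and a marginal difference for proportions are compatible choices, and the precision argument for adjustment is weaker here: Table 18 gives 99.5% power for seroconversion, Table 19 93.2% for the GMC ratio. The by-country, by-group rates in the per-protocol set, if laid out as in Template 10 with N and n, supply what a stratified difference with the usual weights needs. A sensitivity row would leave the confirmatory criterion unchanged, and no rule is offered for the case where the two intervals disagree. Making the stratified interval confirmatory would require a reworded criterion and a pooling rule for small countries, with no gain in power.

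**Conclusion.** The concern does not hold. Protocol and SAP agree on a valid interval for the seroconversion difference, and Table 18 reproduces within 0.3 points. With countries balanced, stratifying changes the half-width by about 0.03 to 0.11 points, leaves power at 99.8-99.9%, and gives a slightly higher error (2.63% against 2.34% at 76.8/93.9%). The largest adverse error in the table, about 4.0%, needs three things at once: the two most extreme Table 16 rates in two equal countries, a 3-point imbalance in one chosen direction, and a true difference exactly at the margin. Nothing in the documents supports such drift.

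These sizes rest on country rates assumed from different studies, since none are given by country, and on a common difference across countries. They would need another look only if the planned enrolment and deviation tables showed a marked country imbalance between arms.
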